5.2.6 Planned use of linked data and benefit to patients in England

In addition to patient level Index of Multiple Deprivation (IMD) data and the CPRD Aurum Ethnicity Record as previously described, we will use Hospital Episode Statistics (HES; NHS Digital, 2022) data to access hospital admission data. The Office for National Statistics (ONS) death registration data will provide mortality records. Linkages are necessary to identify patient outcomes and healthcare utilisation.

5.2.7 Definition of the study population

All individuals in the CPRD Aurum database, regardless of age, with a first recorded index tracer condition between 01/01/2015 to 31/12/2022 and 24 months prior registration in CPRD Aurum. We will compare outcomes for patients with a recent history of A&G to those with direct referral, stratified by tracer condition. A&G and direct referrals will be obtained from primary care records in the 24 months prior to index (first diagnosis) date. Patients with both A&G and direct referral will be classified based on whichever happened first. We will include age at index date, gender, neighbourhood deprivation, geographical region, and ethnicity, as common covariates for all analyses as well as covariates (e.g. multiple long term conditions) specific to each tracer condition. There is no comparison or control group.

The tracer conditions will be informed from the work in WP1, including interviews with PCCs, and the experiences and advice of our PPIE and Stakeholder groups.

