5.2.5 Sample size considerations

Taking multiple sclerosis as the example condition, we expect around 11,000 people to have a new diagnosis between 2015 and 2022 in CPRD (based on reported national incidence of 7,000 per year,²⁴ CPRD covering 20% of UK population and study period of 8 years). Based on the feasibility study in SLE, if 5% received A&G then we could detect a hazard ratio of 1.15 or more with 90% power at a 5% significance level. We expect other conditions to be more prevalent.

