5.3 DATA / STATISTICAL ANALYSIS

For WP2a, the outcome for those with an A&G and/or direct referral recorded will be the time to diagnosis from the first recorded A&G or direct referral to index diagnosis date. We will calculate median (interquartile range) days to diagnosis from first recorded A&G or direct referral code and incidence rates per 1,000 person years and present with 95% confidence intervals. We will use flexible parametric survival analysis to compare A&G and direct referral on time to diagnosis. Flexible parametric survival analyses are preferred to Cox proportional hazards regression as they allow easier modelling of time-dependent effects and the ability to determine absolute risks of outcome. Exposure' will be the initial method of referral (A&G, direct referral) prior to index date. Hazard ratios will be presented as unadjusted and adjusted for covariates with 95% confidence intervals (CI).

For WP 2b, individuals with each index condition will be categorised as i) A&G only, ii) direct referral only, iii) A&G and direct referral, iv) no recorded A&G or direct referral in the 24 months before diagnosis:

- negative binomial or zero-inflated negative binomial regression will be used to estimate incidence rate ratios for the number of consultations, referrals and prescriptions in primary care, and number of outpatient appointments,
- robust Poisson regression will be used to compare A&E and unplanned admission in secondary care;
- flexible parametric survival analysis will estimate hazard ratios for mortality.

Rates or ratios will be presented as unadjusted and adjusted for covariates with 95% CI.

As part of the Study Within A Project (SWAP) (see Section 8), the impact of multimorbidity and frailty on decision to use A&G and its outcomes will be considered by including multimorbidity and frailty (defined by Charlson comorbidity index/number of prescriptions and electronic frailty index) as predictors and moderators of A&G outcome in the models.

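### WP2a includes only patients diagnosed within 24 months of A&G or referral, so its rates are not incidence and its hazard ratio is biased in a direction and by an amount that the Protocol does not fix

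*Protocol*

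**What the plan says.** Protocol 5.2.7 defines the WP2 population as people "with a first recorded index tracer condition between 01/01/2015 to 31/12/2022 and 24 months prior registration in CPRD Aurum". Exposure and start date are sought backwards from that diagnosis: "A&G and direct referrals will be obtained from primary care records in the 24 months prior to index (first diagnosis) date". Where both routes occur, "Patients with both A&G and direct referral will be classified based on whichever happened first".

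Protocol 5.3 takes as the WP2a outcome the "time to diagnosis from the first recorded A&G or direct referral to index diagnosis date". It plans median and interquartile range, "incidence rates per 1,000 person years and present with 95% confidence intervals", and unadjusted and adjusted hazard ratios from flexible parametric survival models. Those models are preferred to Cox regression because "they allow easier modelling of time-dependent effects and the ability to determine absolute risks of outcome".

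The confounding, missing-data and limitations sections (5.3.1 to 5.3.3) cover unmeasured confounding, recording quality, misclassification and uncoded portals. They do not mention selection on the outcome or truncation of the interval.

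**The concern.** Protocol 1.1.2 names the effect of A&G on time to diagnosis of significant disease as unknown, so slow or missed diagnosis is the harm of interest. The WP2a cohort cannot show its worst forms:

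- A patient diagnosed 30 months after A&G drops out of WP2a. If there was another contact inside the window, the patient re-enters with a later start date and possibly in the other exposure group.
- A patient who is never diagnosed, or who dies undiagnosed, is absent.

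The remaining intervals are right-truncated. Methods for a cohort followed forward, such as rates per person-time, absolute risks and ordinary hazard ratios, then do not estimate what their names say. WP2 results are intended for policy makers and commissioners (Protocol 10.1.2), so a hazard ratio near 1 could be taken as reassurance that the design cannot give.

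**Working it through.** **1. The plan's own figure.** Protocol 5.2.5 expects "we expect around 11,000 people to have a new diagnosis between 2015 and 2022 in CPRD", with 5% receiving A&G, a detectable hazard ratio (HR) of 1.15, 90% power and 5% significance (two-sided assumed).

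- Patients: 7,000 × 0.20 × 8 = 11,200, against about 11,000.
- Events needed (Schoenfeld): (1.960 + 1.282)² / (0.05 × 0.95 × (ln 1.15)²) = 10.507 / (0.0475 × 0.019533) ≈ 11,325.
- Power at 11,000 events: √(11,000 × 0.0475) × 0.1398 − 1.960 = 1.235, which is 89.2%.

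The figure is reproduced only if every diagnosed patient counts as an event. This fits the reading that nobody is censored.

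**2. Rate and risk among the diagnosed.** With n patients, all with the event, the rate is n / (sum of intervals) = 1 / mean interval. The proportion diagnosed by month 24 is n / n = 100% in each group.

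Illustration (assumed): direct referral leads to diagnosis in 50% and A&G in 25%, with the same exponential timing, median 6 months. Then λ = ln 2 / 6 = 0.1155 per month, 1/λ = 8.656 months, and the share of eventual diagnoses made by 24 months is 1 − 2⁻⁴ = 0.9375.

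- True 24-month risks: 0.50 × 0.9375 = 47% and 0.25 × 0.9375 = 23%. In the diagnosed-only cohort both are 100%.
- Full-cohort person-months per patient to month 24: 12 + 0.5 × 0.9375 × 8.656 = 16.06 for direct referral and 18 + 0.25 × 0.9375 × 8.656 = 20.03 for A&G. The rates are about 350 and 140 per 1,000 person-years.
- Diagnosed-only mean interval: 8.656 − 24 × 0.0625 / 0.9375 = 7.056 months in both groups, so both rates are about 12,000 / 7.056 = 1,701.
- By simulation, the full-cohort HR of 0.43 becomes 1.00.

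**3. HR under the 24-month limit alone.** The Protocol gives no interval distribution, so everything here is assumed: exponential intervals, proportional hazards, constant A&G use, and a Cox HR as proxy for the flexible parametric one. The share beyond 24 months is exp(−(ln 2 / median) × HR × 24).

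| Direct-referral median | Beyond 24 months, direct | Beyond 24 months, A&G (HR 0.80) | Fitted HR, true 0.80 |
|---|---|---|---|
| 3 months | 0.4% | 1.2% | 0.82 |
| 9 months | 15.7% | 22.8% | about 0.91 |
| 12 months | 25% | 33% | about 0.93 |

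Simulation runs at 9 to 12 months spread over about 0.90 to 0.96.

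For the effect size of the sample-size section taken as a delay (1 / 1.15 = 0.87), with 11,000 events:

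| Direct-referral median | Fitted HR | Power |
|---|---|---|
| 3 months | 0.88 | 82% |
| 6 months | 0.92 | 53% |
| 12 months | 0.95 | 19% |
| 24 months | 0.98 | 8% |

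With short, tightly spread intervals (Weibull shape 1.5, median 3 months), 0.80 stays 0.80 and 0.87 stays 0.87.

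**4. Adding the calendar limit.** Diagnoses end on 31/12/2022, and Protocol 1.2 says the pandemic accelerated A&G use. A&G requests made late in the period can enter only if the interval is short.

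- A&G share rising linearly fivefold over 2013 to 2022 (assumed): a true 1.00 becomes about 1.05, 1.07 and 1.09 at medians of 3, 6 and 12 months. A true 0.80 at 12 months becomes about 1.01.
- Steeper linear rise (assumed): a true 1.00 becomes 1.09, 1.14 and 1.16, and a true 0.87 becomes 0.97, 1.05 and 1.11.

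With constant A&G use, a true 1.00 stays at 1.00.

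**The case against.** The best defence is that WP2 is labelled descriptive and hypothesis generating, is to be designed iteratively, and looks deliberately at recent history. Within that scope, medians, quartiles and the cumulative curve describe the interval correctly for patients diagnosed within 24 months. If intervals are mostly short, the truncation bias is negligible. That stands, and it limits the point. It does not cover the incidence label or an adjusted, powered hazard ratio from truncated times, and the limitations section does not warn the reader.

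Three stronger readings do not hold:

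- A reader might infer that the hazard ratio always shrinks towards 1, so that the plan leans to finding no harm. That follows only from a common 24-month limit with proportional hazards and constant A&G use. The rise in A&G that the Protocol describes can push the ratio above 1.
- A reader might infer that the outputs have no meaning. They have one, but it is not the incidence or risk of diagnosis after A&G or referral.
- A reader might infer that absolute risks are a planned output. Section 5.3 mentions "the ability to determine absolute risks of outcome" only as a reason for the choice of model. The listed outputs are medians, rates and hazard ratios.

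**Conclusion.** The defect is real and follows from 5.2.7 and 5.3 alone. WP2a selects on the outcome and truncates the interval at 24 months, so all patients have the event, none is censored, and long delays and missed diagnoses are invisible. Two consequences need no assumption: the rate equals 1 / mean interval among the diagnosed, and a 24-month risk is 100% in both groups.

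The hazard ratio is open to bias whose direction and size depend on the interval distribution and on the growth of A&G, neither of which the Protocol gives. Over the ranges assumed, the bias runs from almost none to enough to make a real delay look like no effect or faster diagnosis. The individual simulated values illustrate that range and do not predict the result. The point should be settled before the WP2 data application, because undiagnosed patients cannot be studied if their data are not requested.

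**What to change.** - **5.3, description:** present WP2a as intervals among patients diagnosed within 24 months of A&G or referral. Keep median and interquartile range. Stop presenting incidence rates, and do not derive absolute risks of diagnosis, from this cohort.
- **5.3, comparison:** fit the model with a likelihood that conditions on T ≤ 24 months and on T ≤ 31/12/2022 minus the referral date, and adjust for calendar time of referral. Referrals before 2015 also need the matching lower limit, since their diagnosis must fall on or after 01/01/2015.
- **5.3.3:** state the selection on diagnosis and the truncation as a limitation. Say that first recorded contact means first within the 24-month window.
- **If rates, absolute risks or a hazard ratio for delayed or missed diagnosis are wanted:** specify a forward cohort in the WP2 data application. It starts at the first A&G or direct referral relevant to the tracer condition, is followed to diagnosis, and is censored at death, deregistration or end of data.

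A five-year look-back should not become the main analysis. For a 2015 diagnosis it reaches back to 2010, while Protocol 1.2 says A&G has been in use since 2012. It would also pick up more unrelated referrals as start dates.

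**Cost:** revised wording and more analysis. The conditional likelihood cannot restore missed diagnoses. The forward cohort needs a larger data request and a definition of a relevant referral. Section 5 says WP2 permissions are still to be sought, so no data are lost.

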To derive the comparative prevalence and incidence of elective referrals, direct routine referrals will be determined using codes with a term indicating a referral and defined by consensus of study team to indicate a routine referral to a specialty (i.e. not fast track or referral with an intention to admit / emergency referral). To ascertain A&G events which result in a direct referral, we will determine

NIHR 158681BADGER			
Protocol Version 2.0 18/06/2024	CPMS: 58336	IRAS No: 333799	CPRD ID: 24_004022

referrals within 122 days (4 months) after date of an A&G request. These will be defined as i) a direct referral code defined as above and by ii) linking events in the Referrals table to the Observation table and determining duration of time between the linked observation event and the A&G request date. We will also determine referrals within 122 days (4 months) before an A&G request to see how often A&G requests follow a referral request. As a sensitivity analysis we will repeat for 365 days (12 months) either side of the A&G request date. Code lists for A&G have been derived and used in our CPRD feasibility study (FS_002830). The draft code list for direct referral has also been developed. These code lists are included in the appendix.

Covariates:

- 1) Age at date of A&G request (categorised)
- 2) Sex
- 3) Geographical region
- 4) CCG pseudonym
- 5) Ethnicity group
- 6) Deprivation (based on IMD quintiles)

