5.1 OBJECTIVES, SPECIFIC AIMS & RATIONALE

The aim of this sub-study is to determine outcomes of the use Advice and Guidance (A&G) in primary care. Specific objectives are to:

- 2a. Describe outcomes of tracer conditions following A&G compared to initial direct (non two-week wait)* referral pathways
- 2b. Describe healthcare utilisation and patient burden (for example, further consultations, referrals or prescribing in primary care, unplanned admissions, outpatient appointments) comparing A&G and direct referral pathways.

*non 2 week wait means referrals that are not on fast-track suspected cancer pathways that are used for patients with suspected cancer

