5.2.8 Exposures, outcomes and covariates

1) Advice & Guidance

Please see 4.2.8

2) Direct referral

Please see 4.2.8

NIHR 158681BADGER			
Protocol Version 2.0 18/06/2024	CPMS: 58336	IRAS No: 333799	CPRD ID: 24_004022

3) Tracer conditions

Relevant codes for tracer conditions will be derived from existing code lists (e.g. those already held at Keele and / or using open access lists such as those held by OpenCodelists) or developed and validated through consensus of EHR researchers and clinical academics within the study team and the EHR Research Group at Keele University, a group led by co-applicants KJ and KM. This research group has set procedures for developing code lists. Codes for covariates and outcomes will be derived in a similar process.

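### In WP2a the 'initial method of referral' is really the first A&G or routine referral code, so a patient who began on a fast-track or emergency route for the same problem is assigned to a later pathway with a late clock start

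*Protocol*

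**What the plan says.** Objective 2a (Protocol 5.1) is to "Describe outcomes of tracer conditions following A&G compared to initial direct (non two-week wait)* referral pathways". Section 5.3 says that the WP2a exposure "will be the initial method of referral (A&G, direct referral) prior to index date", and that time to diagnosis runs from the first recorded A&G or direct referral.

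For both exposure definitions, 5.2.8 says only "Please see 4.2.8". In 4.2.8 a direct referral is a routine referral to a specialty, "not fast track or referral with an intention to admit / emergency referral".

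The population in 5.2.7 is everyone "with a first recorded index tracer condition between 01/01/2015 to 31/12/2022 and 24 months prior registration in CPRD Aurum". The look-back is stated as "A&G and direct referrals will be obtained from primary care records in the 24 months prior to index (first diagnosis) date". When both types of code are present, "Patients with both A&G and direct referral will be classified based on whichever happened first".

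WP2b (5.3) uses four groups over the same 24 months: A&G only, direct referral only, both, and neither.

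Section 1.1.2 describes emergency referral and the suspected-cancer fast-track as routes separate from the two elective options.

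**The concern.** The exposure is named as the first step a patient took, but the rule compares only two kinds of code. Taking fast-track and emergency codes off the direct-referral list removes those codes. It does not remove the patients who have them. A patient whose route to the tracer diagnosis began as an emergency or on a fast track, and who later has an A&G request or routine referral, enters WP2a as though the later code were the start. Two things are then wrong for that patient: the pathway label and time zero, since investigation may already have been under way.

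At stake is the A&G versus direct referral hazard ratio for time to diagnosis. If such patients are more common in one arm, or the late start is longer there, the ratio moves away from its true value for a reason unrelated to either pathway. There is a lesser issue of interpretation in WP2b: the group with neither code will mix people with no recorded referral and people referred only by fast track or as an emergency.

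**Working it through.** **1. Apply the rule as written.** Definitions are from 4.2.8 through 5.2.8, look-back and ordering from 5.2.7, clock and groups from 5.3.

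| Coded sequence in the 24 months before diagnosis | WP2a exposure | WP2a clock starts | WP2b group |
|---|---|---|---|
| A&G, then diagnosis | A&G | A&G | i |
| Routine referral, then diagnosis | Direct | Routine referral | ii |
| Emergency or fast-track, then A&G, then diagnosis | A&G | A&G (late) | i |
| Emergency or fast-track, then routine, then diagnosis | Direct | Routine referral (late) | ii |
| Emergency or fast-track, then both elective codes | Whichever elective code came first | That code (late) | iii |
| Emergency or fast-track only | Not in WP2a | – | iv |
| No referral code | Not in WP2a | – | iv |

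Rows 3 to 5 are the problem for WP2a. Rows 6 and 7 share one group in WP2b. Nothing in 5.2.4 to 5.3.3 separates any of them. HES linkage is planned for outcomes and utilisation (5.2.4, 5.2.6), not for assigning the pathway.

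**2. Reproduce the plan's figure (5.2.5).** Cases: 7,000 × 0.20 × 8 = 11,200, stated as around 11,000. Schoenfeld power, two-sided 5% (sidedness is not stated), A&G share 5%:

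power = Φ(√(E × 0.05 × 0.95) × ln 1.15 − 1.96)

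E = 11,000 gives 89.2% and E = 11,200 gives 89.7%. Exactly 90% needs 11,325 events. The stated 90% is reproduced, provided every diagnosed patient counts as an event with a qualifying code.

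**3. Size of the bias: a hand calculation.** The documents give no share of affected patients and no delay, so every input here is an assumption. Take no true difference, a mean of 180 days to diagnosis in both arms, shares mA (A&G) and mD (direct) affected, and their clock late by L days. The crude rate ratio, A&G versus direct, is

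(180 − mD × L) / (180 − mA × L)

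- mA = mD = 5%, any L: 1.00
- mA = 20%, mD = 5%, L = 90: 175.5 / 162 = 1.083 (L = 30 gives 1.026)
- mA = 5%, mD = 20%, L = 90: 162 / 175.5 = 0.923 (L = 30 gives 0.975)

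**4. Size of the bias: a simulation.** Again no true effect. Times are exponential with mean 8 months, truncated at 24 months. Affected patients have mean 2 or 4 months before truncation. Arms are equal with 500,000 patients each, and the hazard ratio comes from a Cox fit (standard error of the log hazard ratio 0.002).

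| Affected, A&G / direct | HR, mean 2 months | HR, mean 4 months |
|---|---|---|
| 5% / 0% | 1.04 | 1.03 |
| 10% / 0% | 1.08 | 1.05 |
| 20% / 0% | 1.17 | 1.09 |
| 10% / 5% | 1.04 | 1.03 |
| 5%, 10% or 20% in both | 1.00 | 1.00 |
| 0% / 10% | 0.93 | 0.96 |
| 0% / 20% | 0.86 | 0.91 |

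**5. Power if affected patients are left out** (formula of step 2, A&G share kept at 5%). Removing 5% leaves E = 10,450: power 87.6%, detectable hazard ratio at 90% power 1.157. Removing 10% leaves E = 9,900: 85.8% and 1.161. Removing 20% leaves E = 8,800: 81.5% and 1.172.

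**The case against.** The strongest reply is that section 5.3 defines its own term. The initial method is the first of A&G and direct referral, and the routine-only code list honours the non-two-week-wait qualifier in objective 2a. WP2 is exploratory, is to be designed iteratively, and has its data application still to come. A reader might infer that the protocol contradicts itself here. It does not. What is missing is a rule, and the label claims more than the rule delivers. But 5.2.7 already fixes eligibility, ordering and time zero, so the gap lies in what is written and is not merely detail left for later.

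Frequency is the second point, and it stands. The fast-track route is for suspected cancer, and the conditions the protocol names (multiple sclerosis in 5.2.5; SLE, MND and endometriosis in 9.1) are not cancers. The final tracers are not chosen. How many patients are affected is unknown, and emergency referral may matter more than fast track.

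Third, a reader might infer that the hazard ratio will be pushed in favour of A&G, or by as much as the 1.15 target. The documents support neither. Equal contamination gives 1.00, the direct arm may be the one affected, and reaching 1.15 takes about 20% in one arm, none in the other, and very short times.

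Fourth, a reader might infer that group iv distorts the WP2b pathway comparison. Its make-up cannot affect the contrast between A&G and direct referral. It affects only what group iv itself means.

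Finally, the limitations in 5.3.3 expect misclassification to occur at random, and 5.3.1 acknowledges unmeasured severity. Neither covers this mechanism, which follows from the classification rule and, where coded, can be detected in the same primary care records.

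**Conclusion.** The point holds as a gap in definition. Followed exactly, the WP2a rule assigns some patients to a pathway they did not start on, with a late time zero. In WP2b the same patients sit in groups i to iii, and those with only a fast-track or emergency referral sit in group iv, where they affect the reading of that group alone. The sample size calculation is not in error on this point.

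The size and sign of any bias cannot be derived from the documents. Under the assumptions in the working it is nil with equal shares. It is about 1.05–1.17 on the hazard ratio with 10–20% of the A&G arm affected and none of the direct arm, and about 0.96–0.86 with the arms exchanged. The definition gap is certain; its consequence will depend on the tracer condition. It is worth closing before the WP2 data application, because it can be measured cheaply then.

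**What to change.** In 5.2.7:

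- Also identify coded fast-track and emergency or intention-to-admit referrals in the 24-month look-back that are relevant to the tracer condition, by specialty or morbidity code.
- Report, by arm, how many precede the first A&G or direct referral.
- Repeat the WP2a and WP2b pathway comparisons without those patients.
- Keep such referrals when they come after the first A&G or direct referral, as consequences of that pathway.
- Report group iv in two parts: fast-track or emergency only, and no referral recorded.

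The restriction to condition-relevant codes matters. Excluding on any such code would drop eligible patients for unrelated referrals, plausibly more often those with multiple long-term conditions, who are the focus of the study within a project (section 8).

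The cost is an additional code list and a smaller set in the repeated analysis, with power of about 86–88% if 5–10% are removed. Building the routine list already requires a judgement on which referral codes are fast-track or emergency, and approval for WP2 has yet to be sought. Emergency contacts without a GP code will still be missed, and the report should say so.

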5.2.4 Outcomes to be measured

For WP2a, the outcome for those with an A&G and/or direct referral recorded will be the time to diagnosis from the first recorded A&G or direct referral to index diagnosis date.

For WP2b, outcomes will be guided by our PPIE and Stakeholder groups as well as emerging results from interviews with PCC's. They are likely to include in the 12 months following referral:

- i. Number of consultations recorded in primary care;
- ii. Number of prescriptions recorded in primary care;
- iii. Number of referrals recorded in primary care;
- iv. AE attendance recorded in HES AE
- v. Number of additional outpatient appointment recorded in HES outpatients
- vi. Overnight unplanned hospital admission recorded in HES APC (admitted patient care);
- vii. Mortality recorded in ONS.

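### WP2 fixes required registration and age at diagnosis although exposure starts up to 24 months earlier, so no equal pre-exposure baseline is guaranteed and undated covariates may run into the outcome window

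*Protocol*

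**What the plan says.** Protocol 5.2.7 admits patients "with a first recorded index tracer condition between 01/01/2015 to 31/12/2022 and 24 months prior registration in CPRD Aurum". It equates the index date with first diagnosis and searches for the exposure backwards from it: "A&G and direct referrals will be obtained from primary care records in the 24 months prior to index (first diagnosis) date". On covariates it says "We will include age at index date, gender, neighbourhood deprivation, geographical region, and ethnicity, as common covariates for all analyses", adding others "as well as covariates (e.g. multiple long term conditions) specific to each tracer condition". Age is the only one of these with a date.

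Sections 5.2.4 and 5.3 run the WP2a outcome from the first recorded A&G or direct referral to the index diagnosis. The likely WP2b outcomes in 5.2.4 cover the 12 months after referral and include "Number of prescriptions recorded in primary care". For the SWAP, 5.3 plans on "including multimorbidity and frailty (defined by Charlson comorbidity index/number of prescriptions and electronic frailty index) as predictors and moderators of A&G outcome", with no measurement date or window. Section 5.3 also divides WP2b into four groups. The fourth has neither A&G nor direct referral in the 24 months before diagnosis.

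**The concern.** A baseline should be fixed at or before the start of exposure, from records available over the same length of time for everyone. Here eligibility and age are fixed at the WP2a event, not at time zero. The exposure search may use up the whole of the required registration. A patient referred 23 months before diagnosis needs only one month of earlier record, and one referred a month before diagnosis must have 23. The shortfall grows with the outcome, so adjustment for prior comorbidity, frailty or prescribing would be least well supported in the patients with the longest delays.

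The second risk concerns the undated variables. Number of prescriptions is named both as a likely WP2b outcome and as part of the multimorbidity and frailty definition, and no window separates the two roles. If the count were taken up to diagnosis, it would include prescriptions issued after the pathway began. Some of these would be the very prescriptions counted as the outcome. Adjusting for it would remove part of the difference WP2b is meant to describe, and the SWAP moderators would partly be consequences of the pathway.

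**Working it through.** **The plan's own figure.** The protocol gives no number on this point. The only WP2 calculation (5.2.5) uses HR 1.15, 5% A&G, 90% power and 5% significance (taken as two-sided). Events = (1.960 + 1.282)² / [0.05 × 0.95 × (ln 1.15)²] ≈ 11,325. This agrees with the stated 11,000 or so (7,000 × 0.20 × 8 = 11,200); power at 11,000 is 89.2%. The point below changes this only through the number of eligible patients.

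**Guaranteed history before exposure.** Put the referral at month 0 and diagnosis at month T, with 0 ≤ T ≤ 24 (5.2.7). Registration is required from month T − 24, so guaranteed record before month 0 is 24 − T months.

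**Overlap if a 12-month prescription count ended at diagnosis.** The 12-month length and the diagnosis end-point are assumptions, since neither is stated. The count covers [T − 12, T] and the outcome covers [0, 12]. Their intersection runs from max(0, T − 12) to min(12, T). Its length is T months if T ≤ 12, and 12 − (T − 12) = 24 − T months if T > 12.

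| T (months) | Guaranteed history | Overlap |
|---|---|---|
| 3 | 21 | 3 |
| 6 | 18 | 6 |
| 12 | 12 | 12 |
| 18 | 6 | 6 |
| 23 | 1 | 1 |

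At T = 12 the covariate and the outcome are the same prescriptions.

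**Effect on the WP2b prescription rate ratio (simulation, all inputs assumed).** About 200,000 patients, 20% A&G, no confounding; prescribing rises 30% after direct referral and 60% after A&G; exponential delay truncated at 24 months; gamma-Poisson prescribing. The model is a negative binomial regression of the 12-month post-referral count, adjusted for log(1 + prior count). The true ratio is 1.60 / 1.30 = 1.23.

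- Count ending at referral: 1.23.
- Count ending at diagnosis: 1.15, 1.11, 1.10 and 1.09 for underlying median delays of 3, 6, 9 and 12 months.
- Share of the log effect lost: 1 − ln 1.15 / ln 1.23 ≈ 33%, up to 1 − ln 1.09 / ln 1.23 ≈ 58%.

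With 5% A&G, the share assumed in 5.2.5, the results are similar.

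**Effect on the WP2a hazard ratio (simulation, inputs assumed).** 40 runs of 11,000 patients, 5% A&G, median delay 6 months before truncation at 24.

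- Age at diagnosis in place of age at referral changes the A&G hazard ratio by at most 0.0014 (0.8639 to 0.8653).
- A prescription count ending at diagnosis in place of referral changes it by at most 0.0037 (0.8805 to 0.8842), with prescribing 1 to 3 times higher after referral.

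**The case against.** The strongest reply is that the covariate sentence dates age alone. Gender and ethnicity do not depend on the date, and referral route is unlikely to change deprivation or region, so none of these is a plausible mediator. For multimorbidity, frailty and prescriptions the date is absent, not wrong, and covariate windows are commonly left to an analysis plan. Section 5.3 also speaks of how multimorbidity and frailty affect the decision to use A&G, which points to measurement before that decision. WP2 is to be designed iteratively, its outcomes are only likely ones, and results will be shown unadjusted as well as adjusted, so attenuation would be visible. WP1a does date age at the A&G request, but it has no diagnosis cohort, so the contrast is not a contradiction.

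Most of this stands. A reader might infer that WP2 measures all its covariates after exposure and so adjusts away the pathway effect. The text does not support that: only age is tied to diagnosis, it can differ from age at referral by at most two years, and it barely moves the hazard ratio.

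The reply does not reach the registration rule. That rule is stated, it defines the cohort to be drawn, and an analysis plan cannot recover history that was never required. Twenty-four months is a minimum and many patients may have more, but nothing secures it. Nor does the reply remove the double role of prescriptions.

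**Conclusion.** The point holds in two parts of different strength. By the stated rules, registration and age are anchored at diagnosis while exposure and both outcome clocks start earlier. Guaranteed pre-exposure record is therefore 24 − T months and shrinks as the WP2a outcome grows. This follows from the text without assumptions.

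The overlap of covariate and outcome is conditional. It arises only if the undated comorbidity, frailty and prescription measures follow the one anchor WP2 gives. For the prescription outcome it could then be material: 1.23 falling to about 1.15 to 1.09, given the assumed 12-month count, prescribing rises and delays. In the assumed WP2a scenarios the shift was below 0.004. The larger figures therefore apply to one WP2b outcome under stated assumptions and should not be read as the expected bias in WP2 generally. The change is cheap and worth making before the WP2 data application.

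**What to change.** In 5.2.7 and 5.3, for patients with an A&G or direct referral:

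- set baseline at the first A&G or referral;
- require a fixed registration look-back before that date, for example 12 months;
- measure age, MLTC/Charlson and frailty only from records on or before that date, and the prescription count strictly before it.

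For the WP2b group with neither pathway there is no such date. State a separate anchor for it, or leave it out of contrasts that use the referral-anchored window.

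No new data are needed, and WP2 permissions are still to be sought (introduction to section 5). The cost is patients without enough registration before referral, a number the documents do not give. A 12-month look-back means up to 24 + 12 = 36 months of registration before diagnosis. If the present 24-month rule is kept beside it, only patients with T above 12 months can be lost, because 24 − T is already at least 12 for the rest. A 24-month look-back before referral would make the present rule redundant and the registration requirement independent of T, but would need up to 48 months and lose more patients. A count under each option in the feasibility data would settle the choice.
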